8.4.2 Unanticipated Problem Reporting

To satisfy the requirement for prompt reporting, all Ups will be reported using the following timeline:

- UPs that are SAEs will be reported to the IRB and to the Statistical and Data Coordinating Center (SDCC)/study Sponsor within 24 hours of the investigator becoming aware of the event per the above describe SAE reporting process.
- Any other UP will be reported to the IRB and to the SDCC/study Sponsor within 3 days of the investigator becoming aware of the problem.

9. STATISTICAL CONSIDERATIONS

9.1 Statistical Hypotheses

The primary null hypothesis tests whether the time-to-recovery differs between the experimental and control arms.

Table 4. Hypothesis tests of interest for ACTT-1 and ACTT-2

R=remdesivir, B=baricitinib and C=placebo

ACTT-1	
Primary hypothesis	R vs C
ACTT-2	
Primary hypothesis	R+B vs R

A key secondary hypothesis tests the null distribution of a similar distribution of 8-point ordinal scale at Day 15. For this, the parameter of interest is the “common odds ratio,” which quantifies the shift in the severity distribution resulting from treatment. For an efficacious treatment, an odds ratio greater than 1 quantifies an improvement in disease severity; a value of 2 indicates a bigger improvement than a value of 1.25. The null hypothesis to be tested is that the odds of improvement on the ordinal scale is the same for the control and experimental treatment arms (i.e., the common odds ratio is 1). It is worth noting that, for large sample sizes, the test based on the proportional odds model is nearly the same as the Wilcoxon rank sum test.

9.2 Sample Size Determination

Primary endpoint: The log-rank test will be used to compare treatment arms with respect to time to recovery. For the log-rank test, the two key determinants of power are the total number of events (i.e., recoveries) E and the treatment-to-control ratio of the rate of recovery, R. The number of events required for power $1 - \beta$ to detect a recovery rate ratio of θ using a two-tailed test at alpha=0.05 is approximately

$$E = \frac{4(1.96 + z_\beta)^2}{\{\ln(\theta)\}^2},$$

where z_β is the $100(1 - \beta)$ th percentile of the standard normal distribution.

Appendix B - ACTT-2: Baricitinib/Remdesivir vs Remdesivir

The force of recovery (sometimes loosely referred to as the “recovery ratio”) is the analogue of the hazard ratio and the term “recovery rate ratio” is the analogue of the hazard ratio in this setting. A recovery rate ratio of 1.31 was reported in Cao, Wang, Wen et al. (2020) for a lopinavir/ritonavir trial that used time to improvement by 2 categories as primary endpoint. A preliminary review of data from ACTT-1 demonstrated a recovery rate ratio 1.312. It is unlikely the second component of treatment will have a similar effect size. Therefore a recovery ratio of 1.25 is assumed for this trial. A total of 723 recoveries are needed for a recovery ratio of 1.25 with 85% power. [Table 5](#) provides power for various recovery rate ratios. The study will accrue until approximately 723 recoveries have been achieved. The date of study closure will be estimated based on enrollment rate and recovery/enrollment percentages. If approximately 70% of participants recover, the total sample size will be 1032.

Table 5. Number of recoveries needed for 85% power assuming a type I error rate of 5% for various recovery ratios.

Recovery rate ratio (θ)	Number of recoveries needed for 85% power
1.20	1080
1.25	723
1.30	523
1.35	400
1.40	318

Key secondary: A sample size can be computed using an (assumed) ordinal scale distribution for the control arm and the odds ratio representing clinical improvement. The odds ratio represents the odds of improvement in the ordinal scale for combination treatment relative to the control arm [Whitehead, 1993]. The sample size to detect a given odds ratio for 1:1 randomization using a 2-tailed test at level α is given by

$$\frac{12(z_{\alpha/2} + z_{\beta})^2}{\lambda^2(1 - \sum_{i=1}^K p_i^3)},$$

where λ is the log odds ratio, p_i is the overall probability (combined over both arms) of being in the i th category of the K ordinal outcomes, and $z_{\alpha/2}$ and z_{β} are the $1 - \alpha/2$ and $1 - \beta$ quantiles of the standard normal distribution.

[Table 6](#) displays five scenarios considered for outcome probabilities in the control arm for sample size determination. There is significant uncertainty with these assumptions given the limited data available. [Table 6](#) shows a range of sample sizes for odds ratios ranging from 1.25 to 2.5 for 85% power. For 90% power, increase the sample size by 17%. [Table 8](#) displays the probabilities of being in different categories of the ordinal scale under an odds ratio of 1.75. A total sample size of 396 gives approximately 85% power to detect an odds ratio of 1.75 using a 2-tailed test at level $\alpha = 0.05$. The categories of the 8-point ordinal scale are:

- Death;

- Hospitalized, on invasive mechanical ventilation or ECMO;
- Hospitalized, on non-invasive ventilation or high flow oxygen devices;
- Hospitalized, requiring supplemental oxygen;
- Hospitalized, not requiring supplemental oxygen – requiring ongoing medical care (COVID-19 related or otherwise);
- Hospitalized, not requiring supplemental oxygen – no longer requires ongoing medical care;
- Not hospitalized, limitation on activities and/or requiring home oxygen;
- Not hospitalized, no limitations on activities.

Note that the data elements contributing to this scale will be captured separately, in order to facilitate different orderings or groupings, as might arise if external data provide information about the clinical course of disease.

Table 6: Possible scenarios for the distribution of ordinal outcomes for the control arm at Day 15.

	Anticipated	Different scenarios for control arm				
		Scenario 1	Scenario 2	Scenario 3	Scenario 4	Scenario 5
Severity Outcome	more mild disease ← → more severe disease					
	outcome (%)	outcome (%)	outcome (%)	outcome (%)	outcome (%)	outcome (%)
Death	2	1	1	2	3	
Hospitalized, on mechanical ventilation or ECMO	1	1	1	1	3	
Hospitalized, on non-invasive ventilation or high flow oxygen devices	2	1	1	2	4	
Hospitalized, requiring supplemental oxygen	7	2	5	5	9	
Hospitalized, not requiring supplemental oxygen – requiring ongoing medical care (COVID-19 related or otherwise)	8	5	7	17	23	
Hospitalized, not requiring supplemental oxygen – no longer requires ongoing medical care	10	9	10	20	25	
Not hospitalized, limitation on activities and/or requiring home oxygen	30	36	35	25	18	
Not hospitalized, no limitations on activities	40	45	40	28	15	

Table 7: Sample size calculations for scenarios in Table 6 for a two-arm study assuming 85% power, a two-sided type I error rate of 5%, and various true odds ratios.

True odds ratio	Total sample size				
	Scenario 1	Scenario 2	Scenario 3	Scenario 4	Scenario 5
1.25	2420	2554	2459	2293	2252
1.5	744	786	755	700	684
1.75	396	419	401	370	360
2.0	262	277	265	243	236
2.25	194	206	196	179	173
2.5	154	163	155	141	136

Table 8. Treatment ordinal outcome proportions under an odds ratio of 1.75 for five scenarios in Table 5 at Day 15.

Severity Outcome	Scenario 1		Scenario 2		Scenario 3		Scenario 4		Scenario 5	
	Control %	Treatment %								
Death	2	1.2	1	0.6	1	0.6	2	1.2	3	1.7
Hospitalized, on mechanical ventilation or ECMO	1	0.6	1	0.6	1	0.6	1	0.6	3	1.8
Hospitalized, on non-invasive ventilation or high flow oxygen devices	2	1.2	1	0.6	1	0.6	2	1.2	4	2.5
Hospitalized, requiring supplemental oxygen	7	4.3	2	1.2	5	3.0	5	3.1	9	5.8
Hospitalized, not requiring supplemental oxygen – requiring ongoing medical care (COVID-19 related or otherwise)	8	5.3	5	3.1	7	4.4	17	11.5	23	17.4
Hospitalized, not requiring supplemental oxygen – no longer requires ongoing medical care;	10	7.2	9	5.9	10	6.8	20	16.2	25	24.4
Not hospitalized, limitation on activities and/or requiring home oxygen	30	26.5	36	29.3	35	30.2	25	25.9	18	22.7

Not hospitalized, no limitations on activities	40	53.8	45	58.9	40	53.8	28	40.5	15	23.6
--	----	------	----	------	----	------	----	------	----	------

Note that columns may not sum to exactly 100 due to rounding errors.

Other key secondaries for testing combination therapy compared to control will be detailed in an addendum SAP

9.3 Populations for Analyses

The primary analysis will be based on an intention-to-treat population, including all subjects randomized. Similarly, safety analyses will be based a modified intent-to-treat population consisting of all subjects who received at least one dose of any investigational product.

9.4 Statistical Analyses

9.4.1 General Approach

This is a double-blind placebo controlled randomized trial testing a superiority hypothesis with a two-sided type I error rate of 5%. Secondary hypotheses have been ordered according to relative importance, with one key secondary hypothesis highlighted. These will be described according to the appropriate summary statistics (e.g., proportions for categorical data, means with 95% confidence intervals for continuous data, median for time-to-event data).

A statistical analysis plan will be developed and filed with the study sponsor prior to unblinding of study and database lock.

9.4.2 Analysis of the Primary Efficacy Endpoint

The primary efficacy analysis is a stratified log-rank test, where stratification is according to baseline disease severity (i.e. protocol defined mild/moderate vs severe disease). Deaths will be considered as never recovering and censored at Day 29. In ACTT2, the analyses conducted will depend on the results from ACTT-1 according to [Table 4](#).

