6.3 Measures to Minimize Bias: Randomization and Blinding

6.3.1 Randomization

Randomization will be stratified by:

- Site
- Severity of illness at enrollment (by ordinal scale)
 - Severe disease:
 - Hospitalized, on invasive mechanical ventilation or ECMO, or
 - Hospitalized, on non-invasive ventilation or high flow oxygen devices.
 - Moderate disease:
 - Hospitalized, requiring supplemental oxygen, or
 - Hospitalized, not requiring supplemental oxygen.

The randomization procedure will be described in the MOP.

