 - Evaluate if subject is neutropenic (absolute neutrophil count <1000 cells/ μ L) ($<1.0 \times 10^3/\mu\text{L}$ or $<1.0 \text{ GI/L}$) and/or lymphopenic (absolute lymphocyte count <200 cells/ μ L) ($<0.20 \times 10^3/\mu\text{L}$ or $<0.20 \text{ GI/L}$)
 - ALT and AST
 - Assess if ALT or AST > 5 times the upper limit of normal.
 - Creatinine (and calculate eGFR).
 - Determine if eGFR $< 30 \text{ ml/min}$ as these subjects are not eligible. Also, subject receiving hemodialysis or hemofiltration are not eligible.
 - Any automated calculation by the clinical laboratory or published formula for this calculation is acceptable. The site should select a formula to be used for all subjects enrolled at the site for the duration of the study.
- Urine or serum pregnancy test (in women of childbearing potential).

Clinical screening laboratory evaluations will be performed locally by the site laboratory. The volume of venous blood to be collected is presented in [Table 3](#).

The overall eligibility of the subject to participate in the study will be assessed once all screening values are available. The screening process can be suspended prior to complete assessment at any time if exclusions are identified by the study team.

Study subjects who qualify will be randomized in the Advantage eClinical system, and all others will be registered as screen failures. The ordinal scale and the NEWS should be done at the time of randomization; the site will need this data to randomize the subject in eClinical. The study team has 24 hours to complete other Day 1 baseline assessments prior to the first study product administration including the collection of OP swab and blood and completing or recording a baseline physical examination that was done.

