9.4.7 Sub-Group Analyses

Subgroup analyses for the primary outcomes will evaluate the treatment effect across the following subgroups: geographic region, duration of symptoms prior to enrollment, baseline disease severity (stratification variable of mild/moderate and severe, as well as ordinal scale of 4/5 vs 6/7) age, race, sex and comorbidities. A forest plot will display confidence intervals across subgroups. Interaction tests will be conducted to determine whether the effect of treatment varies by subgroup.

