9.4.2 Analysis of the Primary Efficacy Endpoint

The primary efficacy analysis is a stratified log-rank test, where stratification is according to baseline disease severity as defined by ordinal scale. Deaths will be considered as never recovering and censored at Day 29. In ACTT-3, the analyses conducted will depend on the results from ACTT-1 according to [Table 4](#).

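### ACTT-2's primary log-rank test pools baseline scores 4 with 5 and 6 with 7; stratifying by the recorded score may recover some power at almost no cost

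*Protocol*

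**What the plan says.** Appendix B 9.4.2 specifies a "stratified log-rank test, where stratification is according to baseline disease severity (i.e. protocol defined mild/moderate vs severe disease"). Section 6.3.1 defines the two groups by ordinal category. The severe group opens with "Hospitalized, on invasive mechanical ventilation or ECMO, or" and continues with high-flow oxygen or non-invasive ventilation. The moderate group holds inpatients on supplemental oxygen and those without it. In the numbering of Appendix C 8.1.2.2, severe is 7 and 6, and moderate is 5 and 4.

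The individual score is available at that moment. Appendix B 8.1.1 states: "The ordinal scale and the NEWS should be done at the time of randomization; the site will need this data to randomize the subject".

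For subgroups, Appendix B 9.4.7 describes baseline severity as "stratification variable of mild/moderate and severe, as well as ordinal scale of 4/5 vs 6/7". Section 9.4.8 compares outcome categories between arms, not baseline scores. Nothing in Appendix B plans a treatment effect for each baseline score.

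The next stage is finer. In Appendix C 9.4.2, "stratification is according to baseline disease severity as defined by ordinal scale". The ACTT-3 SAP, section 8.1.1, makes that 4, 5 or 6, and section 8.1.1 and Table 10 report a hazard ratio for each.

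**The concern.** When subjects with different recovery rates share a stratum, the log-rank comparison is pulled toward no effect, even if the treatment ratio is the same in each. Fast recoverers leave the risk set early, and the mix left behind shifts at different speeds in the two arms. A test that splits those subjects avoids this.

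Two things are at stake. One is some power in the primary test, since the events formula takes the full ratio of 1.25 with no allowance for such dilution. The other is what the trial can say about severity. ACTT-2 tests an anti-inflammatory. Appendix C 1.1 suggests that control of inflammation matters most late in the disease, and Appendix C 9.2 expected score 7 to respond differently from the lower scores. A split that merges 6 with 7 and 4 with 5 cannot show differences within those pairs.

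**Working it through.** **The plan's own figure.** Inputs from Appendix B 9.2 are "using a two-tailed test at alpha=0.05" and "A total of 723 recoveries are needed for a recovery ratio of 1.25 with 85% power". The formula there is E = 4(1.96 + z_β)² / {ln θ}². With z_β rounded to 1.04, E = 4 × 9 / 0.2231² = 36 / 0.04979 = 723. With unrounded z_β (1.036) it is 722. Power at 723 is Φ(√723/2 × 0.2231 − 1.96) = Φ(1.04) = 85.1%. For N, "If approximately 70% of participants recover, the total sample size will be 1032": 723/0.70 = 1032.9. The Appendix B synopsis says 732 recoveries, but 732/0.70 = 1045.7, so N = 1032 goes with 723, which is used here.

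**What has to be assumed.** The documents give no ACTT-2 recovery rate or patient share by baseline score. Apart from the 70% overall, the only recovery proportion assumed for planning is about 90% in ACTT-3, now enrolling scores 4 and 5 (Appendix C 9.2). That suggests recovery depends on severity but says nothing about gaps within a pair.

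**Simulation at 723 expected recoveries.** Ratio 1.25 in every score, exponential recovery times, 28 days, non-recoverers (including deaths) kept at risk throughout, 1:1 allocation within the two strata, two-sided 0.05, 12,000 trials per row, Monte Carlo error about 0.3 to 0.4 points. The last column is 723 × {(1.96 + 1.036)/(1.96 + z of the two-stratum power)}².

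| Control recovery, scores 4/5/6/7 (%) | Share of patients (%) | Four scores | Two strata | Loss (points) | Recoveries for 85%, two strata |
|---|---|---|---|---|---|
| 88/88/45/45 (no gap) | 15/50/20/15 | 85.2 | 85.2 | 0.0 | 719 |
| 88/88/45/45 | 25 each | 84.5 | 84.7 | −0.2 | 730 |
| 93/86/55/35 (moderate) | 15/50/20/15 | 85.0 | 84.3 | 0.7 | 739 |
| 93/86/55/35 | 25 each | 84.3 | 82.9 | 1.4 | 767 |
| 96/82/65/20 (wide) | 15/50/20/15 | 84.6 | 79.9 | 4.7 | 830 |
| 96/82/65/20 | 25 each | 85.1 | 77.3 | 7.8 | 885 |
| 99/75/75/10 (extreme) | 15/50/20/15 | 84.7 | 71.1 | 13.6 | 1026 |
| 99/75/75/10 | 25 each | 84.0 | 62.8 | 21.2 | 1242 |

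The extreme rows are a bound only; nothing in the documents points to gaps of that size.

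**Simulation at N = 1032**, shares 14/48/20/18%, 6,000 trials per setting:

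- 80/78/48/42%: two strata 84.8%, four scores 84.5%; no difference beyond simulation error.
- 85/78/55/35%: 84.5% against 85.1%; loss 0.6 points.
- 95/80/52/25%: 81.0% against 83.7%; loss 2.7 points.

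Also at N = 1032, the 96/82/65/20% setting loses 3.3 points with shares 15/60/15/10% (88.8 − 85.5), 4.4 with 15/50/20/15% (86.9 − 82.5) and 8.2 with equal shares (83.5 − 75.3).

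**Precision of one score.** Take 18% of 1032, or 186 subjects, in score 7. Control recovery of 25% implies 1 − 0.75^1.25 = 30.2% on treatment, so about 51 recoveries. Control recovery of 35% implies 41.6%, so about 71. The 95% interval around 1.25 is 1.25 × exp(±1.96 × 2/√E): 0.72 to 2.16 with 51, 0.79 to 1.99 with 71. Power is about 12% and 15%.

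**The case against.** The strongest defence is that the primary test follows the randomization strata, which is conventional. ACTT-3 is no counter-example, because it randomizes by single score (SAP 4.2.3) and tests by single score; both stages analyse as randomized. That stands, so this is not a departure from good practice. It does not count against finer strata: the four scores nest within the two groups, apart from any mis-stratified subject, so the randomization is still respected.

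Section 9.2 also never says that 1.25 applies within a score. It arrives there by discounting an overall ACTT-1 ratio of 1.312. If 1.25 is the ratio seen by the two-stratum test, 723 recoveries give 85% and finer strata only add to it. This stands.

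On subgroups, main protocol section 9 calls the appendix text a brief summary and leaves detail to each stage's SAP. The SAP supplied covers ACTT-3 only. ACTT-3 shows how an SAP can add detail: Appendix C 9.4.8 names severity by ordinal scale in general terms, and SAP 6.4 and Table 10 supply estimates for each score. The two severity items in Appendix B 9.4.7 may also be distinct: ACTT-3 SAP 6.3 and 6.4 separate the randomized stratum from the actual baseline score because subjects can be mis-stratified. Both points stand.

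Finally, single-score estimates would be weak, as the score 7 intervals show, and the edit reaches the primary test, the interim statistic and the key secondary model. True, but these limit the benefit and add care rather than remove the reason for the change.

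**Conclusion.** The concern holds as an inexpensive improvement, not as an error in the plan. The two-stratum test may lose power if recovery differs between 4 and 5 or between 6 and 7, and if 1.25 is a within-score ratio. The loss runs from nil to about 1 point for small or moderate gaps, and about 3 to 5 points or more for wide gaps (about 8 if patients are spread equally over the scores). These sizes rest on assumed rates and shares. In every setting the four-score test did as well as the two-stratum test, within simulation error.

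A reader might infer more than the documents support:

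- *That the stated 85% power is not reached.* The calculation reproduces, small gaps cost nothing measurable, and the meaning of 1.25 is left open.
- *That the effect in each score is never estimated.* Appendix B does not plan it; the ACTT-2 SAP, not available here, could.
- *That 9.4.7 lists one subgroup twice.* It may mean randomized versus actual severity. On either reading it is still a two-way split.

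**What to change.** Before unblinding, and by staff blind to interim results:

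- In Appendix B 9.4.2, stratify the log-rank test by baseline ordinal score (4, 5, 6, 7) and keep the two-stratum test as a sensitivity analysis.
- In 9.4.3, use the same four-level factor in the proportional odds test.
- In 9.4.7, list scores 4, 5, 6 and 7 separately, say whether the two-way split means randomized or actual severity, and note that single-score estimates, score 7 above all, will be imprecise.
- Carry the change into the ACTT-2 SAP and the DSMB monitoring document, so that the interim review in 9.4.6.2 and the final analysis use the same statistic.

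No new data, patients or change to randomization are needed. The cost is the wording, the matching programming, and a record of when and why the primary test was changed.

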9.4.3 Analysis of the Secondary Endpoint(s)

- 1) The ordinal scale will be used to estimate a proportional odds model by disease strata. The hypothesis test will perform a stratified test to evaluate whether the common odds ratio for treatment is equal to one. The distribution of severity results will be summarized by treatment arm as percentages. Efforts to minimize loss-to-follow-up will be considerable. However, small amounts of missing data may occur. In such cases, subjects without final outcome data will be excluded from the analysis. Sensitivity analyses will evaluate the impact of making different assumptions about missing observations. These analyses will be defined in the SAP.
- 2) Differences in time-to-event endpoints (e.g., time to at least a one category improvement in ordinal scale) by treatment will be summarized with Kaplan-Meier curves and 95%

confidence bounds. The same procedure will be used to compare time to at least a two-category improvement.

- 3) Change in ordinal scale at specific time points will be summarized by proportions (e.g., proportion who have a 1-, 2-, 3-, or 4-point improvement or 1-, 2-, 3-, 4-point worsening).
- 4) Duration of event (e.g., duration of mechanical ventilation) will be summarized according to median days with quartiles.
- 5) Binary data (e.g., incidence of new oxygen use) will be summarized as a percent with 95% confidence intervals. Comparisons between arms will be presented as differences in proportions with 95% confidence intervals.
- 6) Categorical data (e.g., 28-day mortality or ordinal scale by day) may be summarized according to proportions by category and/or odds ratios with confidence intervals.

Procedures for handling missing data, including informative censoring (e.g., a missing duration of oxygen use endpoint due to a death), will be described in the SAP.

9.4.4 Safety Analyses

Safety endpoints include death through Day 29, SAEs and Grade 3 and 4 AEs. These events will be analyzed univariately and as a composite endpoint. Time-to-event methods will be used for death and the composite endpoint. Each AE will be counted once for a given subject and graded by severity and relationship to COVID-19 or study intervention. AEs will be coded using the current version of the Medical Dictionary for Regulatory Activities (MedDRA). AEs will be presented by system organ class, duration (in days), start- and stop-date. Adverse events leading to premature discontinuation from the study intervention and serious AEs will be presented either in a table or a listing.

